3.4 Safety Analysis

All safety analyses will be based on the SS analysis set. A summary will be made per treatment group, and treatment grouping will be made according to subject's actual treatment. The safety analyses include:

- Incidence of surgical site infection (SSI) at the target incision after the phase 1 operation;
- Incidence of full-thickness disruption of target incision after the phase 1 operation;
- Incidence of wound healing delayed event at the target incision after the phase 1 operation;
- Adverse events
- Physical examination

The incidences of SSI/full-thickness disruption/wound healing delayed event at the target incision after the phase 1 operation will be descriptively summarized using the number of cases (percentage), and the 95% CI for each event will be provided per treatment group using the Clopper-Pearson method; in addition, the two-sided Wald 95% confidence interval for the difference in proportion of subjects of each event between treatment groups (experimental group minus control group) will be constructed.

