2.2 Definition of Analysis Sets

The 3 analysis sets in this study are defined as follows:

- The Intent to Treat (ITT) analysis set will include all randomized patients.
- The Per Protocol (PP) analysis set will include subjects in the ITT analysis set who did not have major protocol deviations that have a serious impact on the effectiveness and safety in patients.
- The Safety (SS) analysis set will include all subjects who have been actually treated with the study device.

The ITT and PP analysis sets should be used to analyze the primary effectiveness endpoint and secondary effectiveness endpoints. However, the primary analyses will be based on the ITT analysis set. PP analysis will be regarded as supportive analysis.

The SS analysis set will be used to analyze the safety endpoints.

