3.3.2 Secondary Effectiveness Endpoint Analysis

The secondary effectiveness endpoints will be summarized based on the SS analysis set.

The incidence of mechanical ileus in subjects will be descriptively summarized per treatment group using the number of cases (percentage). The incidence of ileus will be compared between groups using the chi-square test, with the P-value calculated. The two-sided 95% confidence interval for the proportion of subjects with mechanical ileus in the treatment groups will be provided by the Clopper-Pearson method. In addition, the two-sided Wald 95% confidence interval for the difference of two independent proportions (experimental group minus control group) will be constructed.

The extent (no adhesions, grades 1, 2, 3) and severity (no adhesions, grades 1, 2, 3) of adhesions at the target surgical incision site and four abdominal quadrants observed during the phase 2 operation will be descriptively summarized per treatment group using the number of cases (percentage).

In addition, the extent and severity of adhesions at the target incision will be compared between groups using MH (Mantel - Haenszel) chi-square test, with the P-value calculated.

```
proc freq data=data;  
  tables treat*response / chisq cmh nocol nopct;  
  weight count;  
run;
```

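### For safety events or ileus that prove sparse, the planned Wald interval for the between-arm difference is not valid: a reporting-precision fault, not a wrong safety decision

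*SAP*

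**What the plan says.** SAP 3.4 covers SSI, full-thickness disruption (all-layer dehiscence) and delayed healing at the target incision. Within each arm, "the 95% CI for each event will be provided per treatment group using the Clopper-Pearson method". For the contrast between arms it adds "the two-sided Wald 95% confidence interval for the difference in proportion of subjects of each event between treatment groups".

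SAP 3.3.2 treats mechanical ileus the same way: Clopper-Pearson within arms, and for the contrast "the two-sided Wald 95% confidence interval for the difference of two independent proportions (experimental group minus control group) will be constructed". Neither section says what to do when cells are sparse or empty, and neither names an alternative interval.

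Protocol 8.1 lists these endpoints for descriptive summary. No margin or hypothesis is attached to them, and the only acceptance criterion (Protocol 8.5) concerns the primary efficacy endpoint. Neither document gives an expected rate for any of the four events.

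On the population, SAP 3.4 states "All safety analyses will be based on the SS analysis set", and SAP 2.2 defines that set thus: "The Safety (SS) analysis set will include all subjects who have been actually treated with the study device".

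**The concern.** The same counts get a small-sample method within each arm and a large-sample method for the difference. The Wald standard error is built from the observed proportions, so it shrinks towards zero as the counts do, and is exactly zero when neither arm has an event. The printed interval is then narrowest where the data say least.

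Safety is part of the stated primary objective, and for SSI, dehiscence and delayed healing this is the only prespecified measure of uncertainty about the between-arm difference. A table row showing a difference of 0.0 with limits 0.0 and 0.0 would suggest that an excess has been ruled out when it has not.

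**Working it through.** **Sample size behind the intervals.** SAP 1.3.3 gives rates 0.50 and 0.75, one-sided alpha 0.025 and power 90%. With pooled variance under the null:

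n = [1.960·√(2·0.625·0.375) + 1.282·√(0.5·0.5 + 0.75·0.25)]² / 0.25² = (1.342 + 0.848)² / 0.0625 ≈ 76.7, so 77 per arm. Allowing for 30% dropout, 77/0.70 = 110. Both of the plan's figures reproduce. I take 110 per arm as the safety denominator; this is an assumption.

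**Formulas.** Wald: d ± 1.96·√[p₁(1−p₁)/n₁ + p₂(1−p₂)/n₂]. Newcombe combines the two arms' Wilson limits; Miettinen-Nurminen inverts a score test.

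- 0 vs 0: the Wald standard error is 0, so the interval is [0, 0]. The Wilson upper limit for 0/110 is 3.84/(110 + 3.84) = 3.37%, so Newcombe gives ±3.37 points.
- 1 vs 0: d = 0.91 points; SE = √(0.00909·0.99091/110) = 0.905 points; 1.96·SE = 1.77; Wald is -0.86 to 2.68.

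95% intervals at 110 per arm, in percentage points:

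| Events | Wald | Newcombe | Miettinen-Nurminen |
|---|---|---|---|
| 0 vs 0 | 0.00 to 0.00 | -3.37 to 3.37 | -3.39 to 3.39 |
| 1 vs 0 | -0.86 to 2.68 | -2.55 to 4.97 | -2.50 to 4.99 |
| 2 vs 0 | -0.68 to 4.31 | -1.80 to 6.39 | -1.60 to 6.40 |
| 4 vs 0 | 0.14 to 7.13 | -0.40 to 8.98 | 0.19 to 9.00 |
| 5 vs 2 | -1.90 to 7.35 | -2.52 to 8.53 | -2.42 to 8.64 |

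**Coverage.** This is exact enumeration over two binomials at 110 per arm. The true rates are assumed, because the documents give none.

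| True rates | Wald | Newcombe |
|---|---|---|
| 0.5% in both | 99.7% | 99.97% |
| 1% in both | 98.3% | 99.7% |
| 2% in both | 95.8% | 98.1% |
| 1% vs 0.1% (extreme) | 66.8% | 99.9% |
| 1% vs 0.5% | 80.0% | 99.9% |
| 2% vs 0.5% | 88.7% | 99.4% |
| 2% vs 1% | 88.2% | 99.5% |
| 3% vs 1% | 94.5% | 98.0% |
| 5% vs 1% | 92.5% | 97.9% |
| 5% vs 2% | 94.5% | 96.7% |
| 10% vs 5% | 94.9% | 96.0% |

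**Direction of the misses.** At 1% vs 0.1%, the upper limit falls below the true excess in 33.1% of trials, out of 100 − 66.8 = 33.2% misses in all. This is essentially the chance that the higher-rate arm shows no event: 0.99¹¹⁰ = 0.331. At 2% vs 0.5% it is 10.9% of 11.3%. So nearly all misses understate the excess risk in the higher-rate arm, whichever arm that is.

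**Chance of a zero-width interval.** With equal rates it is (1−p)²²⁰: 0.99²²⁰ = 11% at 1%, and 0.995²²⁰ = 33% at 0.5%.

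**Sensitivity to the denominator.** At 77 per arm, 0 vs 0 gives Newcombe ±4.75 points. Wald coverage is then 86.2% at 2% vs 1%, 89.8% at 3% vs 1% and 89.4% at 5% vs 1%, so the near-nominal result at 3% vs 1% depends on having about 110 per arm.

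**The case against.** The strongest reply is that little hangs on these intervals. They are descriptive, and exact limits for each arm are already planned beside them. At 110 per arm the Clopper-Pearson upper limit for no events is 1 − 0.025^(1/110) = 3.3%; for one and two events it is 5.0% and 6.4%. The Miettinen-Nurminen upper limits for 0, 1 and 2 events vs 0 are 3.4, 5.0 and 6.4 points. A careful reader therefore has nearly the right bound in the same table. This stands, and it limits the consequence. It does not make the printed interval for the difference correct.

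Rarity is also an assumption. Nothing in the documents shows that SSI, delayed healing or ileus will be uncommon, so the fault may touch one endpoint, several or none. This stands too. It is also a reason to choose a method that holds across the plausible range.

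A reader might infer that collapse and under-coverage come together. They need not. The 11% and 33% chances of a zero-width interval arise with equal rates, where the true difference is 0, [0, 0] contains it, and Wald over-covers (98.3% and 99.7%). Under-coverage requires unequal rates.

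**Conclusion.** The point holds for sparse counts only. For any of the four endpoints that proves rare, the planned Wald interval for the difference is too short or has no width. At 110 per arm its coverage falls clearly below 95% when the true rates differ and at least one is about 0-2%. It is close to nominal at about 3% vs 1% and above, with some residual shortfall when one arm stays very low (92.5% at 5% vs 1%).

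A reader might infer that the trial's safety conclusion rests on these intervals and could be wrong because of them. The documents do not support that: no safety decision rule, margin or hypothesis refers to them. Nor does the point extend to the primary endpoint, whose planned rates of 0.50 and 0.75 are far from sparse. This is a fault in reporting precision.

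The conclusion rests on assumed event rates and an assumed 110 per arm. The second assumption is not secure. Read literally, the Safety set in SAP 2.2 and Protocol 8.9 contains device-treated subjects only. That leaves no control arm for the comparison planned in SAP 3.4, or for ileus in SAP 3.3.2, which names the same set. The passages must be reconciled before any between-arm interval can be computed.

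**What to change.** In SAP 3.4 and the ileus paragraph of SAP 3.3.2, replace the Wald interval for the difference with either Miettinen-Nurminen (for example `riskdiff(CL=MN)` in PROC FREQ) or Newcombe. Name one in advance: at 4 vs 0 the first excludes zero and the second does not. State that the chosen interval is reported also when neither arm has an event. Separately, reconcile the Safety set definition in SAP 2.2 and Protocol 8.9 with the planned between-arm comparisons.

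The interval change costs one analysis option and one sentence. It does not affect the sample size, data collection or the primary analysis. Intervals become clearly wider for sparse counts: at 1 vs 0 the width goes from 2.68 + 0.86 = 3.54 points to 4.99 + 2.50 = 7.49, about double. They change little when events are common: at true rates of 10% and 5% the mean width is 13.71 points for Wald and 14.67 for Newcombe, about 7% more.

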3.4.1 Adverse events

All adverse events (AEs) will be summarized, and the AEs will be coded using the MedDRA 23.1 dictionary.

An adverse event refers to any detrimental medical events in the course of a clinical trial, whether or not related to the investigational medical device. All AEs, study device failure, and other product problems must be documented in the medical record since the signing of informed consent. In the meantime, for non-serious AEs (excluding ileus-related events) that occur during the period from 30 days after the phase 1 operation to the second hospital admission before the phase 2 operation specified in the protocol, or between Visit 6 and Visit 7, recording and collection are not required if they are assessed as not related or unlikely related to the study device by the study doctor.

The incidences of AEs will be summarized per treatment group and in total using the number of cases (percentage). During the summary of number of cases per PT, if a subject experienced the same AE (distinguished per PT) repeatedly, he/she will be counted once only when calculating the number of cases; During the summary per severity of AE, for the same AE of different severity, the most severe one will be counted when calculating the number of cases.

According to the rules above, the AEs will be summarized generally and per SOC and PT level, and the types of AEs are summarized as follows:

- All AEs recorded during the study period in the EDC
- AEs related to the study product/phase 1 operation/phase 2 operation (including: definitely related, probably related, possibly related, and unlikely related)
- SAE
- Serious AEs related to the study product/phase 1 operation/phase 2 operation (including: definitely related, probably related, possibly related, and unlikely related)

In addition, for AEs that have occurred at least once, the number of cases and percentage will be calculated per SOC, PT, and severity (mild, moderate, and severe), and the same analysis will also be performed for AEs related to the study product.

All AEs will be tabulated to record the AE name (PT), onset date, end date, severity of AE, SAE or not, classification of SAE, relevance with the study product, action taken, and outcome, etc., and the AEs/SAEs leading to death will be tabulated independently.

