### **13. REGULATIONS OF ADVERSE EVENT AND DEVICE DEFECT REPORTING**

#### **13.1. Adverse event**

An AE is defined as any untoward medical occurrence in the process of clinical trial, regardless of its relationship to the investigational medical device.

The investigator should determine whether an AE occurs and determine its relationship to the study device or surgery at each evaluation for the subjects recruited for the clinical study.

All AEs, study device faults and other product problems must be recorded in the medical record and entered in the CRF. All AEs need to be recorded in the EDC system in 2 weeks.

Postoperative pain, fever and laboratory abnormalities is expected and will not be documented as an adverse event unless the Investigator considers the pain or fever to exceed that normally anticipated following the surgery or related to study devices. Also, the adverse event, not including the serious adverse event and ileus event, which is "not relative" or "unlikely related" to the study device and occurred 1. between 30 days after Phase 1 operation and the hospitalization for Phase 2 operation or 2. between Visit 6 and Visit 7 should not be documented.

The severity of adverse event is graded into the following levels:

**Mild:** Existing signs or symptoms have no impact on the usual activities of the subjects, or transient, no treatment required, with no sequel.

**Moderate:** Have an impact on the usual activities of the subjects, with no interference, with possible need of treatment.

**Severe:** Cause the symptom of severe discomfort, resulting in major impact on the usual activities of the subjects, medical intervention or treatment required.

The causal relationship of adverse events should be determined as follows:

**Not related:** The event is definitely not related to the use of product

**Unlikely related:** The time sequence between the use of product and the event shows that the event is unlikely associated,

**Possibly related:** The time sequence between the use of product and the event shows that the event is likely associated, or AE may also be caused by the disease or concomitant treatment of the subjects,

**Probably related:** The time sequence shows the event has temporal relationship to the use of investigational product, or the event is alleviated at the end of use of product, or it is unable to give reasonable explanation to this event according to the disease of the patient,

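### SAP 3.4.1 counts events judged unlikely related as related AEs and SAEs, although non-serious, non-ileus events of that category are not collected for most of follow-up

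*SAP*

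**What the plan says.** Protocol 13.1 sets a five-level causality scale: not, unlikely, possibly, probably and definitely related. For *unlikely related* it says "The time sequence between the use of product and the event shows that the event is unlikely associated". The next level up, *possibly related*, is the first for which it says "The time sequence between the use of product and the event shows that the event is likely associated".

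The same protocol section limits what is recorded. The limit begins "Also, the adverse event, not including the serious adverse event and ileus event", so SAEs and ileus events are outside it. Other events judged not related or unlikely related to the device are left out in two windows: "between 30 days after Phase 1 operation and the hospitalization for Phase 2 operation", and from Visit 6 to Visit 7. SAP 3.4.1 restates the rule for non-serious, non-ileus events in those windows: "recording and collection are not required if they are assessed as not related or unlikely related to the study device".

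Later in the same section, the SAP lists its summary tables. One is "AEs related to the study product/phase 1 operation/phase 2 operation (including: definitely related, probably related, possibly related, and unlikely related". The serious-event table is defined in the same way: "Serious AEs related to the study product/phase 1 operation/phase 2 operation (including: definitely related, probably related, possibly related, and unlikely related". For the breakdown by severity, "the same analysis will also be performed for AEs related to the study product". Related is not redefined there, so that table appears to inherit the four categories. The SAP gives no reason for the grouping, and its section 5 on modifications is marked not applicable.

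**The concern.** One category sits on the unrelated side when the plan decides what to collect, and on the related side when it decides what to tabulate. A related-AE table is normally read as the events the investigator suspects were caused by the product or the surgery. As defined here, it also takes in events that the protocol's scale describes as unlikely to be associated with the product. For non-serious, non-ileus events, the added category is also collected for only part of the time at risk.

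The Protocol (4.3) says the study is meant to support registration in China, and safety is part of the primary objective. The related-event percentages should therefore have a clear meaning.

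**Working it through.** The documents state no related-AE rate, so there is no figure to reproduce. The check compares the texts and then works out how much of follow-up the two windows cover.

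**Step 1. The three rules side by side**

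| Category | Protocol 13.1 scale | Non-serious, non-ileus events in the two windows | SAP 3.4.1 related tables |
|---|---|---|---|
| Not related | definitely unconnected with the product | not collected | out |
| Unlikely related | unlikely associated | not collected | **in** |
| Possibly related | likely associated, or other causes may also explain it | collected | in |
| Probably, definitely related | temporal relation or other support | collected | in |

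The scale and the collection rule both draw their line above *unlikely related*. The SAP tables draw theirs below it. For SAEs and ileus events the third column does not apply, because they are collected whatever their causality.

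**Step 2. Share of follow-up inside the windows**

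Inputs from the documents:
- The first window opens at day 30.
- Phase 2 takes place 3-9 months after Phase 1.
- Visit 6 is 3 days after Phase 2 or at discharge.
- Visit 7 is at 6-7 months, and only if Visit 6 falls at 3-6 months. Otherwise the study ends at Visit 6.

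Assumptions:
- A month is 30.44 days.
- Admission is *a* = 0 to 7 days before Phase 2.
- Visit 6 is 3 days after Phase 2.
- Follow-up *T* runs from Phase 1 to the last visit.

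With Phase 2 on day *P*, window 1 lasts *P* − *a* − 30 days. Window 2, where there is a Visit 7, lasts *T* − (*P* + 3) days. The sum is *T* − 33 − *a*. Without Visit 7, *T* = *P* + 3, and window 1 alone gives the same expression. Such events are therefore collected for 33 + *a* days after Phase 1, whenever Phase 2 takes place.

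| Last visit | *T* (days) | Uncollected, *a* = 0 | Uncollected, *a* = 7 |
|---|---|---|---|
| Visit 7 at 6 months | 182.6 | 149.6/182.6 = 81.9% | 142.6/182.6 = 78.1% |
| Visit 7 at 7 months | 213.1 | 180.1/213.1 = 84.5% | 173.1/213.1 = 81.2% |
| Visit 6, Phase 2 at 6 months | 185.6 | 152.6/185.6 = 82.2% | 145.6/185.6 = 78.5% |
| Visit 6, Phase 2 at 9 months | 277.0 | 244.0/277.0 = 88.1% | 237.0/277.0 = 85.6% |

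Non-serious, non-ileus events unlikely related to the device are thus collected for about 12-22% of follow-up. Neither window applies to possibly-or-higher events.

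**Step 3. Effect on the percentage**

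Let *r* be the subjects with at least one possibly-or-higher event, and *u* those whose only qualifying recorded events are unlikely related. The SAP's percentage is (*r* + *u*)/*n*, and a possibly-or-higher percentage is *r*/*n*. The documents give neither count. As an illustration only, take *n* = 110 device subjects and *r* = 5, so *r*/*n* = 4.5%:
- *u* = 0: no change.
- *u* = 2: 7/110 = 6.4%.
- *u* = 5: 10/110 = 9.1%.
- *u* = 10: 15/110 = 13.6%.

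Subjects whose only unlikely-related events fell inside the windows would add to *u* under the SAP's definition, but they are missing from it. Their number cannot be recovered from the plan.

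**The case against.** The best defence is that no analysis rule is broken. The protocol sets no related/unrelated cut-off for tables, and a rule that limits recording need not fix how events are grouped in a summary. Excluding only *not related* is a cautious choice, stated in the table heading itself. The all-AE and all-SAE tables do not depend on it. The AE listing shows relation to the product, so product-related events can be regrouped. One could add that the product is said to be absorbed within four weeks (Protocol 5.1.1) and the first window opens at day 30. That may explain the collection rule, but the documents do not say so.

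Most of this stands, and it keeps the point small. It does not remove it. Caution is a reason to include a category that is fully collected, and this one is not, for non-serious, non-ileus events. The heading discloses the categories but not the gap in collection.

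Three stronger readings are tempting and are not supported:
- *The tables overstate device toxicity.* This holds only against a possibly-or-higher definition, and only if some subjects have unlikely-related events alone. Against the SAP's own definition, any uncollected events make the non-serious table too low.
- *The related-SAE table is incomplete.* The collection rule removes no SAEs and no ileus events.
- *Late wound events judged unlikely related are lost.* Surgical site infection, all-layer dehiscence and delayed healing are scheduled at Visits 4 to 7 without a causality filter and have their own analyses in SAP 3.4.

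**Conclusion.** The mismatch is real and minor. SAP 3.4.1 labels as related a category that the protocol's scale describes as unlikely associated with the product. This applies to AEs and SAEs, and apparently to the product-related severity table. That scale is worded for the product, while the table headings also cover the two operations, so the mismatch is clearest for relation to the product.

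For non-serious, non-ileus AEs there is also a conflict with the collection rule. The resulting percentage is neither a rate of suspected reactions nor a complete count under the definition used. The 78-88% figure rests on the timing assumptions above, and a longer Phase 2 stay before Visit 6 would lower it somewhat. The effect on the reported rate cannot be sized from the documents and may be nil.

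The safety tables are descriptive, and the success criterion uses only the primary endpoint, so the primary test is unaffected.

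**What to change.** In SAP 3.4.1, before database lock:
- Define related as possibly, probably or definitely related in the related-AE, related-SAE and product-related severity tables.
- Show *unlikely related* as its own row for AEs and SAEs.
- Add a footnote that non-serious, non-ileus events judged unlikely related to the device were not collected between day 30 and Phase 2 admission, or between Visit 6 and Visit 7. Word it by relation to the device, because that is what the collection rule uses.

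The cost is a change of SAP wording, one table row and a footnote, with no new data. The headline related count becomes less inclusive, but the separate row keeps the information in view.
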